8.1.9. Pregnancy

Female subjects who become pregnant after the vaccination may continue the study at the discretion of the investigator.

While pregnancy itself is not considered an AE or SAE, any adverse pregnancy outcome or complication or elective termination of a pregnancy for medical reasons will be recorded and reported as an AE or a SAE.

090177e19088c6d6\Approved\Approved On: 11-Mar-2019 09:45 (GMT)

Note: The pregnancy itself should always be recorded on an Exposure During Pregnancy (EDP) form.

The following should always be considered as SAE and will be reported as described in Sections 8.3.1 and 8.3.2:

- Spontaneous pregnancy loss, including:
 - spontaneous abortion, (spontaneous pregnancy loss before/at 22 weeks of gestation)
 - ectopic and molar pregnancy
 - stillbirth (intrauterine death of foetus after 22 weeks of gestation).

Note: the 22 weeks cut-off in gestational age is based on WHO-ICD 10 noted in the EMA Guideline on pregnancy exposure [EMA 2006]. It is recognized that national regulations might be different.

- Any early neonatal death (i.e. death of a live born infant occurring within the first 7 days of life).
- Any congenital anomaly or birth defect (as per [CDC MACDP] guidelines) identified in the offspring of a study subject (either during pregnancy, at birth or later) regardless of whether the foetus is delivered dead or alive. This includes anomalies identified by prenatal ultrasound, amniocentesis or examination of the products of conception after elective or spontaneous abortion.

Furthermore, any SAE occurring as a result of a post-study pregnancy AND considered by the investigator to be reasonably related to the investigational vaccine will be reported to Pfizer as described in Section 8.3.2. While the investigator is not obligated to actively seek this information from former study participants, he/she may learn of a pregnancy through spontaneous reporting.

8.2. Detecting and recording adverse events, serious adverse events and pregnancies

8.2.1. Time period for detecting and recording adverse events, serious adverse events and pregnancies

All AEs starting one month (i.e. 30 days) following administration of the dose of study vaccine must be recorded into the appropriate section of the eCRF, irrespective of intensity or whether or not they are considered vaccination-related.

The time period for collecting and recording SAEs will begin at the receipt of study vaccine and will end one month (i.e. study end) following administration of the dose of study vaccine for each subject. See Section 8.3 for instructions on reporting of SAEs.

SAEs that are related to the investigational vaccine and any event related to lack of vaccine efficacy will be collected and recorded from the subject's last visit in the

persistence study MENACWY-TT-043 EXT:036 Y2, 3, 4, 5 (112148) until the subject is discharged from the study.

In addition to the above-mentioned reporting requirements and in order to fulfil international reporting obligations, SAEs that are related to study participation (i.e. protocol-mandated procedures, invasive tests, a change from existing therapy) will be collected and recorded from the time the subject consents to participate in the study until she/he is discharged from the study.

All AEs/SAEs leading to withdrawal from the study will be collected and recorded from the time of the receipt of study vaccine.

The time period for collecting and recording pregnancies will begin from administration of the study vaccine and will end one month (i.e. study end) following administration of the study vaccine. See Section [8.3](#) for instructions on reporting of pregnancies.

Occurrences of NOCIs (e.g. auto-immune disorders, asthma, type 1 diabetes, allergies) will be recorded from administration of the study vaccine dose until one month (i.e. study end) post administration of the study vaccine, whether or not they are considered to be possibly related to vaccine administration. Medical documentation of the events will be reported either as an unsolicited AE or as an SAE as appropriate in the eCRF.

Occurrences of GBS will be recorded from administration of the study vaccine dose until one month (i.e. study end) post administration of the study vaccine. Clinical details should be obtained as outlined in the 'Potential immune mediated disorders: standard questionnaires and list of preferred terms'. All occurrences of GBS have to be reported as SAEs.

An overview of the protocol-required reporting periods for AEs, SAEs, and pregnancies is given in [Table 14](#).

Table 14 Reporting periods for adverse events, serious adverse events and pregnancies

Study activity	Last visit done in study MenACWY-TT-036 (109069) or in the study MENACWY-TT-043 EXT:036 Y2, 3, 4, 5 (112148)	Pre-vacc ^{*,1}	Booster Vacc. ¹	4 days (Days 0-3) Post-vacc. ¹	31 days (Days 0-30) Post-vacc. ¹
			Visit 1 Month 120	Month 120 + 3 days	Visit 2 Month 121
Reporting of solicited local and general Adverse Events (AEs)					
Reporting of unsolicited AEs					
Reporting of NOCI ²					
Reporting of GBS ³					
Reporting of all Serious Adverse Events (SAEs) ⁴					
Reporting of pregnancies ⁵					
Recording of SAEs related to study vaccination and any event related to lack of vaccine efficacy since the previous visit. ^{4,6}					
Recording of SAEs related to study participation					

*i.e Consent obtained.

¹ Vacc.: vaccination; Pre-vacc.: pre-vaccination; Post-vacc.: post-vaccination.

² NOCI = New Onset Of Chronic Illness(es) (e.g. autoimmune disorders, asthma, type I diabetes and allergies [a non-exhaustive list of NOCIs is provided in Table 13]). These AEs are collected from the day of the booster vaccination (Day 0) until one month [30 days] post-booster vaccination.

³ In the event of Guillain Barré Syndrome (GBS), subjects should be contacted to obtain clinical details as outlined in the 'Potential immune mediated disorders: standard questionnaires and list of preferred terms'. All occurrences of GBS have to be reported as SAEs.

⁴ All SAEs are collected from the day of the booster vaccination (Day 0) until one month [30 days] post-booster vaccination. Occurrence of meningococcal diseases should be documented in the SAE report in the eCRF.

⁵ Pregnancies occurring between the booster vaccination (Day 0) and one month after vaccination (Day 30) will be recorded. If, after having been vaccinated, a subject is found to have been pregnant at vaccination, the pregnancy will be recorded as an exclusion criterion.

⁶ Subjects will be questioned at entry of study C0921005 (MENACWY-TT-101 EXT:036 Y10) whether any SAEs occurred since the subject's last visit in MenACWY-TT-036 (109069) study or in the MenACWY- TT-043 EXT:036 Y2, 3, 4, 5 (112148) persistence study.

090177e19088c6d6\Approved\Approved On: 11-Mar-2019 09:45 (GMT)

8.2.2. Post-Study adverse events and serious adverse events

A post-study AE/SAE is defined as any event that occurs outside of the AE/SAE reporting period defined in [Table 14](#). Investigators are not obligated to actively seek AEs or SAEs in former study participants. However, if the investigator learns of any SAE at any time after a subject has been discharged from the study, and he/she considers the event reasonably related to the investigational vaccine/product, the investigator will promptly report the SAEs to Pfizer.

8.2.3. Evaluation of adverse events and serious adverse events

8.2.3.1. Active questioning to detect adverse events and serious adverse events

As a consistent method of collecting AEs, the subject should be asked a non-leading question such as:

‘Have you felt different in any way since receiving the vaccine or since the previous visit?’

When an AE/SAE occurs, it is the responsibility of the investigator to review all documentation (e.g. hospital progress notes, laboratory and diagnostics reports) relative to the event. The investigator will then record all relevant information regarding an AE/SAE in the eCRF. The investigator is not allowed to send photocopies of the subject’s medical records to Pfizer instead of appropriately completing the SAE form and CRF. However, there may be instances when copies of medical records for certain cases are requested by Pfizer. In this instance, all subject identifiers will be blinded on the copies of the medical records prior to submission to Pfizer.

The investigator will attempt to establish a diagnosis pertaining to the event based on signs, symptoms, and/or other clinical information. In such cases, the diagnosis should be documented as the AE/SAE and not the individual signs/symptoms.

8.2.3.2. Assessment of adverse events

8.2.3.2.1. Assessment of intensity

The intensity of the following solicited AEs will be assessed as described:

Table 15 Intensity scales for solicited symptoms

Adverse Event	Intensity grade	Parameter
Pain at injection site	0	None
	1	Mild: Any pain neither interfering with nor preventing normal every day activities.
	2	Moderate: Painful when limb is moved and interferes with every day activities.
	3	Severe: Significant pain at rest. Prevents normal every day activities.
Redness at injection site		Record greatest surface diameter in mm
Swelling at injection site		Record greatest surface diameter in mm
Fever*		Record greatest temperature in °C
Headache	0	Normal
	1	Mild: Headache that is easily tolerated
	2	Moderate: Headache that interferes with normal activity
	3	Severe: Headache that prevents normal activity
Fatigue	0	Normal
	1	Mild: Fatigue that is easily tolerated
	2	Moderate: Fatigue that interferes with normal activity
	3	Severe: Fatigue that prevents normal activity
Gastrointestinal symptoms (nausea, vomiting, diarrhoea and/or abdominal pain)	0	Gastrointestinal symptoms normal
	1	Mild: Gastrointestinal symptoms that are easily tolerated
	2	Moderate: Gastrointestinal symptoms that interfere with normal activity
	3	Severe: Gastrointestinal symptoms that prevent normal activity

* Fever is defined as temperature $\geq 37.5^{\circ}\text{C}$ for oral, axillary or tympanic route, or $\geq 38.0^{\circ}\text{C}$ for rectal route. The preferred route for recording temperature in this study will be oral.

The maximum intensity of local injection site redness/swelling will be scored as follows:

0	:	None
1	:	> 0 - \leq 20 mm
2	:	> 20 - \leq 50 mm
3	:	> 50 mm

The maximum intensity of fever will be scored as follows for oral/axillary or tympanic route:

0	:	<37.5°C
1	:	$\geq 37.5^{\circ}\text{C}$ — $\leq 38.5^{\circ}\text{C}$
2	:	>38.5°C— $\leq 39.5^{\circ}\text{C}$
3	:	>39.5°C

The investigator will assess the maximum intensity that occurred over the duration of the event for all unsolicited AEs (including SAEs) recorded during the study. The assessment will be based on the investigator's clinical judgement.

The intensity should be assigned to one of the following categories:

- 1 (mild) = An AE which is easily tolerated by the subject, causing minimal discomfort and not interfering with everyday activities.
- 2 (moderate) = An AE which is sufficiently discomforting to interfere with normal everyday activities.
- 3 (severe) = An AE which prevents normal, everyday activities
Such an AE would, for example, prevent attendance at work/school and would necessitate the administration of corrective therapy.

An AE that is assessed as Grade 3 (severe) should not be confused with a SAE. Grade 3 is a category used for rating the intensity of an event; and both AEs and SAEs can be assessed as Grade 3. An event is defined as 'serious' when it meets one of the pre-defined outcomes as described in Section 8.1.2.

8.2.3.2.2. Assessment of causality

The definitions for 'NO' and 'YES' have been written in such a way that all events that have been attributed a 'NO' can be pooled with events which in the primary vaccination study were determined to be 'not related' or 'unlikely to be related' to vaccination. Those events that are attributed a 'YES' can be pooled with those events that in the past were determined to have a 'suspected' or 'probable' relationship to vaccination in the primary vaccination study.

The investigator is obligated to assess the relationship between investigational vaccine/product and the occurrence of each unsolicited AE (including SAEs) and for general solicited AEs. The investigator will use clinical judgement to determine the relationship. Alternative plausible causes, such as natural history of the underlying diseases, concomitant therapy, other risk factors, and the temporal relationship of the event to the investigational vaccine/product will be considered and investigated. The investigator will also consult the CDS to determine his/her assessment.

There may be situations when a SAE has occurred and the investigator has minimal information to include in the initial report to Pfizer. However, it is very important that the investigator always makes an assessment of causality for every event prior to submission of the SAE report to Pfizer. The investigator may change his/her opinion of causality in light of follow-up information and update the SAE information accordingly. The causality assessment is one of the criteria used when determining regulatory reporting requirements.

In case of concomitant administration of multiple vaccines, it may not be possible to determine the causal relationship of general AEs to the individual vaccines administered. The investigator should, therefore, assess whether the AE could be causally related to vaccination rather than to the individual vaccines.

All solicited local (injection site) reactions will be considered causally related to vaccination. Causality of all other AEs should be assessed by the investigator using the following question:

Is there a reasonable possibility that the AE may have been caused by the investigational vaccine/product?

- YES : There is a reasonable possibility that the vaccine(s) contributed to the AE.
- NO : There is no reasonable possibility that the AE is causally related to the administration of the study vaccine(s). There are other, more likely causes and administration of the study vaccine(s) is not suspected to have contributed to the AE.

If an event meets the criteria to be determined as ‘serious’ (see Section 8.1.2), additional examinations/tests will be performed by the investigator in order to determine ALL possible contributing factors for each SAE.

Possible contributing factors include:

- Medical history.
- Other medication.
- Protocol required procedure.
- Other procedure not required by the protocol.
- Lack of efficacy of the vaccine, if applicable.
- Erroneous administration.
- Other cause (specify).

8.2.3.3. Assessment of outcomes

The investigator will assess the outcome of all unsolicited AEs (including SAEs) recorded during the study as:

- Recovered/resolved.
- Recovering/resolving.
- Not recovered/not resolved.
- Recovered with sequelae/resolved with sequelae.
- Fatal (SAEs only).

8.2.3.4. Medically attended visits

For each solicited and unsolicited symptom the subject experiences, the subject will be asked if he/she received medical attention defined as hospitalisation, or an otherwise unscheduled visit to or from medical personnel for any reason, including emergency room visits. This information will be recorded in the eCRF.

8.2.3.5. Adverse events of specific interest

AEs of specific interest for safety monitoring include:

- NOCIs such as autoimmune diseases, asthma, type I diabetes and allergies. Refer to Section 8.1.8.1 for a non-exhaustive list of illnesses that can be recorded as NOCI.
- GBS.
- Meningococcal disease.

Occurrences of NOCIs will be reported up to one month after the vaccine dose regardless of seriousness and whether or not they are considered to be possibly related to the treatment administration. Medical documentation of the events will be reported either as an unsolicited AE or as an SAE as appropriate in the eCRF.

Occurrences of GBS will be reported up to one month after the vaccine dose. Clinical details should be obtained as outlined in the 'Potential immune mediated disorders: standard questionnaires and list of preferred terms'. All occurrences of GBS have to be reported as an SAE.

Occurrences of meningococcal disease will be reported during the entire course of the study up to the study end and have to be reported as an SAE.

8.3. Reporting of serious adverse events, pregnancies, and other events

8.3.1. Prompt reporting of serious adverse events, pregnancies, and other events

SAEs, including those due to GBS and invasive meningococcal disease, that occur in the time period defined in Section 8.2 will be reported promptly within the timeframes described in Table 16, once the investigator determines that the event meets the protocol definition of a SAE.

Pregnancies that occur in the time period defined in Section 8.2 will be reported promptly within the timeframes described in Table 16, once the investigator becomes aware of the pregnancy.

Table 16 Timeframes for submitting serious adverse event, exposure during pregnancy and other events reports

Type of Event	Initial Reports		Follow-up of Relevant Information on a Previous Report	
	Timeframe	Documents	Timeframe	Documents
All serious adverse events (SAEs)	24 hours*	paper SAE report	24 hours*	paper SAE report
Pregnancies	24 hours*	paper SAE and EDP reports	24 hours*	paper SAE and EDP reports
Guillain Barré Syndrome	24 hours*	paper SAE report	24 hours*	paper SAE report
Invasive Meningococcal disease	24 hours*	paper SAE report	24 hours*	paper SAE report

* Timeframe allowed after receipt or awareness of the information.

8.3.2. Completion and transmission of SAE reports

Once an investigator becomes aware that a SAE has occurred in a study subject, the investigator (or designee) must complete the information in the paper SAE report WITHIN 24 HOURS. The SAE report will always be completed as thoroughly as possible with all available details of the event. Even if the investigator does not have all information regarding a SAE, the report should still be completed within 24 hours. Once additional relevant information is received, the report should be updated WITHIN 24 HOURS.

The investigator will always provide an assessment of causality at the time of the initial report.

8.3.3. Completion and transmission of pregnancy reports

Once the investigator becomes aware that a subject is pregnant, the investigator (or designee) must complete the required information onto the EDP report WITHIN 24 hours of awareness of the exposure.

Note: Conventionally, the Estimated Gestational Age (EGA) of a pregnancy is dated from the first day of the Last Menstrual Period (LMP) of the cycle in which a woman conceives. If the LMP is uncertain or unknown, dating of EGA and the estimated date of delivery should be estimated by ultrasound examination and recorded in the pregnancy report.

8.3.4. Updating of SAE and pregnancy information after *removal of write access to the subject's eCRF*

When additional SAE or pregnancy information is received after removal of the write access to the subject's eCRF, new or updated information should be recorded on a paper report, with all changes signed and dated by the investigator. The updated report should be faxed to Pfizer within the designated reporting time frames specified in Table 16.

090177e19088c6d6\Approved\Approved On: 11-Mar-2019 09:45 (GMT)

8.3.5. Regulatory reporting requirements for serious adverse events

The investigator will promptly report all SAEs to Pfizer in accordance with the procedures detailed in Section 8.3.1. Pfizer has a legal responsibility to promptly notify, as appropriate, both the local regulatory authority and other regulatory agencies about the safety of a product under clinical investigation. Prompt notification of SAEs by the investigator to Pfizer is essential so that legal obligations and ethical responsibilities towards the safety of other subjects are met.

Investigator safety reports are prepared according to the current Pfizer policy and are forwarded to investigators as necessary. An investigator safety report is prepared for a SAE(s) that is both attributable to the investigational vaccine/product and unexpected. The purpose of the report is to fulfil specific regulatory and GCP requirements, regarding the product under investigation.

8.4. Follow-up of adverse events, serious adverse events, and pregnancies

8.4.1. Follow-up of adverse events and serious adverse events

8.4.1.1. Follow-up during the study

After the initial AE/SAE report, the investigator is required to proactively follow each subject and provide additional relevant information on the subject's condition to Pfizer (within 24 hours for SAEs; refer to [Table 16](#)).

All SAEs documented at a previous visit/contact and designated as not recovered/not resolved or recovering/resolving will be reviewed at subsequent visits/contacts until the end of the study.

All AEs documented at a previous visit/contact and designated as not recovered/not resolved or recovering/resolving will be reviewed at subsequent visits/contacts until study end.

NOCIs and GBS documented at a previous visit/contact and designated as not recovered/not resolved or recovering/resolving will be reviewed at subsequent visits/contacts until study end.

8.4.1.2. Follow-up after the subject is discharged from the study

The investigator will follow subjects:

- with SAEs, or subjects withdrawn from the study as a result of an AE, until the event has resolved, subsided, stabilised, disappeared, or until the event is otherwise explained, or the subject is lost to follow-up.
- with other AEs of specific interest (i.e. NOCIs, GBS, meningococcal disease) until one month after the vaccine dose or until the subject is lost to follow-up.

If the investigator receives additional relevant information on a previously reported SAE, he/she will provide this information to Pfizer using a paper SAE and/or EDP report as applicable.

Pfizer may request that the investigator performs or arranges the conduct of additional clinical examinations/tests and/or evaluations to elucidate as fully as possible the nature and/or causality of the AE or SAE. The investigator is obliged to assist. If a subject dies during participation in the study or during a recognised follow-up period, Pfizer will be provided with any available post-mortem findings, including histopathology.

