3. STUDY DESIGN OVERVIEW

Figure 1 Study design diagram

* MenACWY-TT-43 EXT: 036 Y2, Y3, Y4, Y5

M = Month
 BS = Blood Sample
 Vacc = Vaccination
 TC = Telephone contact
 ESFU = Extended Safety Follow-Up
 N = number of subjects in the primary total vaccinated cohort.

Protocol waivers or exemptions are not allowed with the exception of immediate safety concerns. Therefore, adherence to the study design requirements, including those specified in the outline of study procedures (Section 5.5), is essential and required for study conduct.

- Experimental design: Phase IIIb, open study with two parallel groups: ACWY-TT group: vaccinated with MenACWY-TT in study MenACWY-TT-036 (109069), MenPS group: vaccinated with *Mencevax ACWY* in study MenACWY-TT-036 (109069).

- Duration of the study: Approximately one month for each subject.
 - Epoch 001: Booster starting at Visit 1 (at Booster vaccination[Day 0]) and ending at Visit 2 (one month post-booster vaccination [Day 30])
- Study groups:

Table 1 Study groups and epochs foreseen in the study

Study Groups	Number of subjects	Age (Min - Max) (age unit)	Epoch 001
ACWY-TT	150	20 years –28 years	x
MenPS	50	20 years –28 years	x

*The sample size of this study with respect to the analysis of immunogenicity, reactogenicity and safety post MenACWY-TT booster vaccination is driven by a) the sample size of the primary vaccination study MenACWY-TT-036 (109069) in the participating site and b) assumptions about the enrolment rate at the present extension study. For more information see Section 10.3.

Table 2 Study groups and treatment foreseen in the study

Treatment name	Vaccine/Product name	Study Groups	
		ACWY-TT	MenPS
MenACWY-TT	MenACWY-TT	x	x
	NaCl *	x	x

*The lyophilized pellet of MenACWY-TT vaccine is to be reconstituted with the supplied saline solution.

- Control: uncontrolled.
- Vaccination schedule: At Visit 1 (Month 120 post primary vaccination), one dose of MenACWY-TT conjugate vaccine will be administered to all subjects in both study groups.
- Treatment allocation: The subjects in this study will be allocated to the same groups as in the vaccination study MenACWY-TT-036 (109069). Subjects will be allocated a new container number, but will retain the same subject number as in MenACWY-TT-036.
- Blinding: Study will be conducted in an open manner.

Table 3 Blinding of study epochs

Study Epochs	Blinding
Epoch 001	Open

- Sampling schedule: Two blood samples for each subject enrolled:

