5.6.15.1. Recording of GBS and New Onset of Chronic Illnesses (NOCIs)

- Please refer to Section 8.2 for procedures for the investigator to record GBS and NOCIs. Refer to Section 8.3 for guidelines on how to report GBS and NOCIs.
- In the event of GBS, subjects should be contacted to obtain clinical details as outlined in the ‘potential immune mediated disorders: standard questionnaires and list of preferred term’. All occurrences of GBS have to be reported as SAE(s).
- NOCIs (e.g. auto-immune disorders, asthma, type 1 diabetes, allergies) will be reported as unsolicited AEs or SAE as appropriate.

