8.1.8. Adverse events of specific interest

AEs of specific interest for safety monitoring include the occurrence of

- NOCIs such as autoimmune disorders, asthma, type 1 diabetes and allergies. Refer to Section 8.1.8.1 for a non-exhaustive list of illnesses that can be recorded as NOCIs.
- GBS (to be reported as a SAE).
- Meningococcal disease (to be reported as an SAE).

See Section 8.2.3.5 for information on recording and reporting of these events.

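### Does Protocol Section 8.4.1.2 cut off follow-up of GBS and meningococcal disease at one month, and leave non-serious new chronic illnesses unfollowed after discharge?

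*Protocol*

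**What the plan says.** Section 8.4.1.2 of the protocol has two bullets on whom the investigator follows after discharge.

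- The first covers subjects "with SAEs, or subjects withdrawn from the study as a result of an AE, until the event has resolved, subsided, stabilised, disappeared". Finding some other explanation, or losing contact with the subject, also ends follow-up under this bullet.
- The second covers subjects "with other AEs of specific interest (i.e. NOCIs, GBS, meningococcal disease) until one month after the vaccine dose". Here too, losing contact ends follow-up.

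Other sections fix how these events are classified. Section 8.2.3.5 states "All occurrences of GBS have to be reported as an SAE". Section 8.1.8 lists "Meningococcal disease (to be reported as an SAE" among the events of specific interest. NOCIs differ: under Section 5.6.15.1 they "will be reported as unsolicited AEs or SAE as appropriate", so some will be non-serious.

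On timing, Section 8.2.1 records NOCIs "until one month (i.e. study end) post administration of the study vaccine", and Section 3 describes a single epoch "ending at Visit 2 (one month post-booster vaccination [Day 30", that is, Day 30. Table 5 allows Visit 2 from 21 to 48 days after Visit 1. A subject seen before Day 30 keeps the diary card and goes on recording to Day 30. Section 8.4.1.1 has unresolved AEs, SAEs, NOCIs and GBS reviewed at later contacts until the study ends.

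**The concern.** Two things look wrong.

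First, a GBS or meningococcal case is always an SAE here, so it meets the first bullet (open-ended), yet the second bullet names it with a fixed limit of one month. An investigator who took the second bullet as the specific rule for those diseases might close the case at Day 30, before its outcome or cause was clear.

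Second, the section is headed as follow-up after discharge, but the limit in its second bullet is the time the protocol elsewhere calls study end. For a non-serious NOCI the bullet therefore seems to promise something and deliver nothing. An event with onset on Day 25 would be followed for 30 - 25 = 5 days, and one on Day 30 for 0 days.

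GBS and NOCIs are named in the secondary safety endpoints. The risk assessment in Section 1.3.1 relies on close monitoring of GBS and points to Section 8.4.1 for it. If the wording led to early closure, outcome and causality information on these events would be lost.

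**Working it through.** The plan gives no figure to reproduce. The check sets the sections side by side, with one small count of days.

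**Step 1. Which rule binds a GBS or meningococcal case?** The inputs are the two bullets of Section 8.4.1.2 and the classification rules in 8.1.8 and 8.2.3.5. Section 6.6 also says meningococcal disease should be reported as an SAE, Section 8.1.5 makes lack of efficacy a criterion for seriousness, and Table 16 requires SAE reports for both GBS and invasive meningococcal disease. Every such case therefore satisfies the first bullet, which has no exception. There are two ways to read the second.

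- If its opening word, other, means events not already covered by the first bullet, no GBS or meningococcal case is left for it, and naming them has no effect.
- If both bullets apply, the investigator must meet both. The second sets a period of follow-up and does not forbid going further. Only following the case "until the event has resolved, subsided, stabilised, disappeared, or until the event is otherwise explained" meets both.

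Followed as written, either reading leads to the same conduct.

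**Step 2. How much follow-up after discharge does the second bullet give a non-serious NOCI?** Take Visit 2 on day v as discharge and Day 30 as the limit. Days after discharge = max(0, 30 - v), with v from 21 to 48 (Table 5).

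| Visit 2 day | 30 - v | Days after discharge |
|---|---|---|
| 21 | 9 | 9 |
| 25 | 5 | 5 |
| 29 | 1 | 1 |
| 30 | 0 | 0 |
| 48 | -18 | 0 |

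The window has 48 - 21 + 1 = 28 possible days. On 9 of them (Days 21-29) the bullet gives 1 to 9 days; on 19 (Days 30-48) it gives none. If discharge means study end as Section 8.2.1 uses the term, it is 0 throughout. So the bullet adds almost nothing to Section 8.4.1.1, as the concern says.

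**Step 3. Is that out of line with the rest of the protocol?** Section 8.4.1.1 reviews all AEs until study end. Section 8.4.1.2 extends this only for SAEs and for subjects withdrawn because of an AE. A non-serious NOCI is thus treated like any other non-serious AE. A serious NOCI, or one that causes withdrawal, goes to the first bullet. The only mismatch is with the section heading.

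**Step 4. Does any planned result depend on it?** Protocol Section 10.2 and SAP Section 3.2 define the endpoint as occurrence of SAEs, GBS and NOCIs on Days 0-30. SAP Sections 5.3.3 and 6.2.4 and Table 11 report percentages of subjects with exact intervals. An event that starts in the window and is recorded counts once, whenever its follow-up ends. The fatal-SAE rows of Table 11 do use outcome, but only for SAEs, which the first bullet follows. The primary endpoint and the sample size are not involved.

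**The case for a change.** The best case for a change is that a safety rule should not have to be rescued by interpretation. The second bullet lists the diseases by name, a list of that kind can be read as the specific rule that displaces the general one, and Section 1.3.1 sends the reader to this very part of the protocol for GBS monitoring. That stands as criticism of the drafting. It does not show a different result, because the mandatory rule for SAEs still applies. Nor can sites diverge: the synopsis and Sections 4.1 and 10.3 describe one participating site in the Philippines.

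On NOCIs, one may object that a chronic illness is poorly described by a few days of observation. Part of this stands. Table 11 also tabulates related and Grade 3 unsolicited AEs, and for a non-serious NOCI still unresolved at study end, causality and maximum intensity would rest on what was known by then. One subject reclassified would move a percentage by 1/150 = 0.7 points in the ACWY-TT group or 1/50 = 2.0 points in the MenPS group, at the planned sizes. The same holds for every non-serious AE in the study, the rule is identical in both groups, and all analyses are descriptive.

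The protocol also has safeguards. The sponsor may ask for further examinations of any AE or SAE, and the investigator must assist (8.4.1.2). An important medical event may be judged serious (8.1.5), which moves it to the first bullet. An unresolved event has its own outcome category (8.2.3.3). Whether non-serious NOCIs deserve longer follow-up is a clinical question on which a statistical review should not rule.

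**Conclusion.** No change to the plan follows. The two bullets of Section 8.4.1.2 do overlap, and the second sits awkwardly under its heading. If the protocol is reopened for another reason, the two bullets can be reconciled with each other and with Sections 8.1.8, 8.2.3.5 and 8.4.1.1 as an editorial matter, with the duration left to the sponsor.

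In size, the effect on counts of GBS, meningococcal disease, SAEs and NOCIs in the Day 0-30 tables is nil, as it is on the primary endpoint and sample size. For non-serious NOCIs the second bullet gives 0 to 9 days after discharge, consistent with how the protocol handles other non-serious AEs. What remains is less outcome detail on a non-serious NOCI unresolved at study end, in a study of about 200 subjects.

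This rests on three assumptions: the investigator applies the SAE bullet to every event the protocol requires to be reported as an SAE; events with onset on Days 0-30 are recorded as Section 8.2.1 requires; and the short end point for non-serious NOCIs is a deliberate choice, as its agreement with Sections 8.2.1, 8.2.3.5 and 8.4.1.1 suggests.
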